Appendix C1: Definitions for Opportunistic Infections

I. Cytomegalovirus:

A. Active Infection:

1. Evidence of active viral replication (positive CMV DNA PCR, evidence of viral infection by on histologic samples)

B. CMV Disease

1. Evidence of Active Infection with attributable symptoms

a. CMV Syndrome: one or more of the following:

1. Fever > 38° C for at least 2 days
2. New or increased malaise
3. Leukopenia
4. ≥ 5% atypical lymphocytes
5. Thrombocytopenia
6. Elevation of hepatic transaminases to 2x ULN plus evidence of viral replication

b. CMV Tissue-invasive disease:

1. Evidence of organ dysfunction in the absence of other documented cause
AND
Evidence of CMV in blood by viral culture or CMV DNA PCR

II. BK Virus:

A. BK Viremia:

1. Quantitative BK viral DNA load in blood above the detection threshold for the laboratory assay on two separate occasions.

B. BK Virus Associated Nephropathy (BKVAN)

1. Renal biopsy associated with BKVAN per current Banff criteria.

III. Other Opportunistic Infections:

A. For definitions of herpes simplex, varicella zoster, Epstein Barr Virus, parvovirus and adenovirus, see American Journal of Transplantation 2006; 6: 262–274

Appendix C2: Treatment of Acute Cellular Rejection

Treatment of Acute Cellular Rejection

Banff 1997 Diagnostic Categories for Acute Cellular Rejection	
Per Banff 1997 diagnostic categories, acute/active cellular rejection (T-cell mediated rejection) histopathological findings include:	
IA: Cases with significant interstitial infiltration (>25% of parenchyma affected) and foci of moderate tubulitis (>4 mononuclear cells/tubular cross section or group of 10 tubular cells)	
IB: Cases with significant interstitial infiltration (>25% of parenchyma affected) and foci of severe tubulitis (>10 mononuclear cells/tubular cross-section or group of 10 tubular cells)	
IIA: Cases with mild to moderate intimal arteritis (v1)	
IIB: Cases with severe intimal arteritis comprising >25% of the luminal area (v2)	
III: Cases with 'transmural' arteritis and/or arterial fibrinoid change and necrosis of medial smooth muscle cells with accompanying lymphocytic inflammation (v3)	

Biopsy Results*	Treatment	Other Requirements	Follow-Up
Borderline rejection	Methylprednisolone 250 mg every 24 hours for 3 doses	 Increase level of maintenance immunosuppression (maximize MMF dosing, increase tacrolimus levels to upper limit of target range.  Assess for non-adherence.  If diabetic, ensure patient is monitoring blood sugars frequently.	 Consider re-biopsy in 7 days if inadequate response to therapy  Patient should have labs weekly  Patient should be seen in clinic with labs one week after completing treatment
Banff '97 1A cellular rejection	Methylprednisolone 500 mg every 24 hours for 3 doses	 Increase level of maintenance immunosuppression (maximize MMF dosing, increase tacrolimus levels to upper limit of target range.  Assess for non-adherence.  If diabetic, ensure patient is monitoring blood sugars frequently.	 Consider re-biopsy in 7 days if inadequate response to therapy  Patient should have labs weekly  Patient should be seen in clinic with labs one week after completing treatment
Banff '97 1B or greater rejection (with viable tissue and ability to obtain maintenance immunosuppressants in order to be adherent going forward)	Thymoglobulin® 1.5 mg/kg/day for 7 doses (10 mg/kg) or 7 days of total suppression Pre-medicate patient with methylprednisolone 500 mg IV x 1 prior to first dose of Thymoglobulin® in addition to acetaminophen and diphenhydramine. May consider giving additional doses of methylprednisolone 250 mg IV prior to subsequent doses. *Always consider patient's prior Thymoglobulin exposure when determining treatment	 Must have daily CBCs for Thymoglobulin® dosing. If WBC 2,000-3,000 or PLT 50,000-75,000, give half dose . If WBC <2,000 or PLT <50,000, hold dose .  Increase level of maintenance immunosuppression (maximize MMF dosing, increase tacrolimus levels to upper limit of target range (tacrolimus levels must be ≥ 8 ng/mL at the time of last Thymoglobulin® dose).  Assess for non-adherence.  Patient must be restarted on anti-microbial prophylaxis including CMV prophylaxis, PCP prophylaxis, and fungal prophylaxis (follow initial protocols with regards to dosing and duration).	 Consider re-biopsy in 7 days if inadequate response to therapy  Patient should have labs weekly  Patient should be seen in clinic with labs one week after completing treatment
Features of AMR and cellular rejection	Please refer to AMR protocol for details.		
Calcineurin inhibitor toxicity with no evidence of rejection (vacuolization of tubules, arteriolar hyalinosis)	Consider patient's candidacy for mTOR conversion. Refer to mTOR conversion/CNI minimization protocol for details.		

* Note: Biopsy should be performed within 48 hours of suspicion for acute rejection

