Adapted from Clinical Therapeutics, Vol. 23, Claxton AJ, Cramer J, Pierce C. A systematic review of the associations between dose regimens and medication compliance, pgs. 1296-1310, Copyright 2001, with permission from Excerpta Medica, Inc.⁴⁴

3. Study design
 1. Single-center, open-label, randomized comparative pilot trial.
 2. There will be 20 subjects in each arm, with a total study size of 40 subjects.
2. Allocation: Four random permuted-blocks of ten with equal arm allocation ratio will be used. Since no other stratification criteria are considered, larger block sizes will be appropriate. In each block, ten random numbers will be generated using SAS 9.4 with a range from zero to ninety nine. Even numbers will be assigned the intervention arm and odd numbers will be assigned the standard of care with resulting 1:1 allocation.
3. Intervention Model: Parallel assignment
4. Masking: This will be an open-label study as masking is not feasible given we are comparing twice-a-day to once-a-day regimen and its effect on adherence.
5. Selection and enrollment of subjects
 1. Inclusion criteria
 1. Male or female adult (≥ 18 years old) with a history of solitary kidney transplant within 3 months (± 2 months) of transplant.
 2. Patients must be capable of understanding the purposes and risks of the study and have the ability to give written informed consent and be willing to participate and comply with the study.
 3. Women of childbearing potential and sexually active males must be willing to use contraception, as indicated in Section 6 of the protocol. Subjects who are not of reproductive potential (status post bilateral tubal ligation, bilateral oophorectomy, hysterectomy, or vasectomy), not sexually active, whose current partner(s) is not of reproductive potential, or whose sexual activity is exclusively homosexual are eligible without requiring the use of contraception.
 2. Exclusion criteria
 1. Patients will be excluded if they are pregnant or nursing females or males with a pregnant female partner
 2. Recipient of multiple organ transplant
 3. Recipient of a non-renal organ
 4. Proteinuria > 800 mg/24 hour
 5. eGFR < 30 ml/min
 6. WBC $\leq 2k/mm^3$

7. $\text{Plt} \leq 50\text{k}/\text{mm}^3$
 8. Triglycerides $> 500 \text{ mg/dL}$
 9. HIV positive (HIV ab +)
 10. Unable to tolerate oral medications
 11. Use of another investigational product within thirty days prior to receiving study medication

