 1. For the first three months (± 2 months) post-transplant, the pool of patients from which subject of this study will be recruited will receive the current standard of care. Standard of care is described as a regimen of tacrolimus IR BID (5-12ng/mL) + MMF 1g BID + prednisone QD Three months (± 2 months) post-transplant and at the time of recruitment, they are randomized to one of the two arms to either receive a complete once-a-day regimen or to receive twice-daily regimen.
 2. Post-randomization, subjects will be converted to one of the two arms, as shown below, and followed for a total period of six months (primary endpoint), or until a terminal end point is reached.
 1. Arm 1: Control-- twice-daily regimen of Envarsus QD (5 - 12ng/mL) + MMF (goal dose 1g BID) + prednisone QD for 6 months

2. Arm 2: Intervention-- once-a-day regimen of Envarsus QD (2- 5ng/mL) + everolimus QD (3-8ng/mL) + prednisone QD for 6 months
 1. Envarsus will be supplied for both Arms from Veloxis Pharmaceuticals
2. Adherence assessment
 1. Adherence to the study intervention will be assessed at all study visits noted on the Schedule of Evaluations (Section 5.1), using the eight point Morisky Medication Adherence Scale (MMAS-8) (17).
5. Clinical and laboratory evaluations
 1. Schedule of evaluations

Data Collection Schedule

Report Form		Baseline	Days Post-Conversion							
			7±2	14±3	30±5	60±7	90±7	120±7	150±7	180±7
Informed Consent Obtained		X								
Randomization		X								
Review of Inclusion and Exclusion Criteria		X								
Medical History		X								
Kidney Transplant Recipient		X								
Vital Signs		X					X			X
Review of Medications and Dosing		X								
Clinical assessment*	Adverse events, dosage and adherence, rejection, infection, hospitalization				X	X	X	X	X	X
	MMAS-8, MMSE Scale, and SF36 (15,16,20)	X								X
Laboratory Assessments	CBC and Chem-7 ¹	X*	O	O	O	O	O	O	O	X*
	Everolimus CO ₂		X*	X*	X*	X*	X	X*	X*	X*
	Tacrolimus CO ₂	X*	X*	X*	X*	X*	X	X*	X*	X*
End of Study										X

X=required; O=optional: data will be collected if performed as standard of care; *=not current standard of care

Footnotes:

1. Includes sodium, potassium, chloride, CO₂, BUN, SrCr, glucose, calcium, WBC, HgB, Hct, platelets
2. Tacrolimus and Everolimus concentrations will be 12- or 24-hour levels , drawn in the morning of each assessment

2. Timing of evaluation
 1. Pre-Randomization Evaluations
Baseline

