4. Recurrent acute rejection is defined as rejection recurring more than two weeks after documented rejection reversal.
5. Opportunistic Infections will be defined according the American Society of Transplant Recommendations for Screening, Monitoring, and

Reporting of Infectious Complications in Immunosuppression Trials in Recipients of Organ Transplantation (Appendix C1).

5. Treatment of Acute rejection:
 1. Acute rejection will be treated per institutional protocol, listed in Appendix C2.

6. Acceptable contraception methods

Option 1 (monotherapy methods):

1. Intrauterine devices (IUDs)
2. Tubal sterilization
3. Patient's partner had a vasectomy

Option 2 (Choice one from category A AND one from category B):

1. Category A:
 - a. Estrogen and progesterone
 - i. Oral contraceptive pill
 - ii. Transdermal patch
 - iii. Vaginal ring
 - b. Progesterone only
 - i. Injection
 - ii. Implant
 - c. Barrier method
 - i. Diaphragm with spermicide
 - ii. Cervical cap with spermicide
 - iii. Contraceptive sponge
2. Category B:
 - a. Male condom
 - b. Female condom
 - c. Diaphragm with spermicide (for use with hormone therapy)
 - d. Cervical cap with spermicide (for use with hormone therapy)
 - e. Contraceptive sponge (for use with hormone therapy)

7. Intervention Discontinuation Evaluations: At the scheduled time of intervention discontinuation (EOT, last date of study), the following evaluations must be completed: vital signs, clinical assessment, CBC, CHEM-7, Everolimus CO, Tacrolimus CO. In case of subject withdrawal from study, the patient will return to standard of care medications and request to continue with final assessment using MMAS-8, MMSE Scale and SF-36 will be discussed with a qualified team member.

8. Adverse Events

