AEs and SAEs will be reported in accordance with the FDA Guidelines for Post-Marketing Reporting of Adverse Events 21 CFR 314.80 and 21 CFR 600.80

<http://www.fda.gov/medwatch/report/regs.htm>. Any serious adverse event or a non-serious adverse event that is related to the study and unexpected will be reported to the FDA, per reporting guidelines, as soon as possible, but no later than 15 working days.. Further, all serious adverse events that are related to the study and are unexpected must be reported to The Medical University of South Carolina IRB within 10 days per The Medical University of South Carolina IRB Unanticipated Problems and Adverse Events Policy and Procedures reporting guidelines.

9. Criteria for intervention discontinuation

1. The intervention will be withheld/discontinued for AE of grade 3 or higher or if requested by the study participant.
2. Additionally, the intervention will be discontinued if the subject meets criteria for the following reasons:
 1. Pregnancy: If a woman becomes pregnant or a male's female partner becomes pregnant while on-study, the subject will be required to instruct investigators immediately.
 2. Loss of graft: Defined as death or need for retransplant. Patients will be deemed a treatment failure and the intervention will be discontinued.\

10. Statistical considerations

1. Outcomes
 1. Primary outcome- Treatment efficacy, defined difference in change from baseline to six month measure by MMAS-8 in both arms.
 2. Secondary objectives
 1. Secondary outcome- Safety outcomes of treatment failure rate, defined as acute allograft rejection with a Banff grade 1A or higher, graft loss, or death at one year post-conversion in both arms.

2. Sample size estimation for the primary outcome

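### For Banff 1B or greater rejection, Appendix C2's tacrolimus floor of 8 ng/mL contradicts the Arm 2 range of 2-5 ng/mL, and its MMF instruction has no counterpart in Arm 2

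*Combined protocol and SAP*

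**What the plan says.** Section 5.5 (Treatment of Acute rejection) reads: "Acute rejection will be treated per institutional protocol, listed in Appendix C2". It makes no exception by arm. Section 5.4 defines acute rejection as a biopsy of Banff grade 1A or greater.

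Section 4.1 gives the regimens. Arm 1 is "twice-daily regimen of Envarsus QD (5 - 12ng/mL) + MMF (goal dose 1g BID) + prednisone QD for 6 months". Arm 2 is "once-a-day regimen of Envarsus QD (2- 5ng/mL) + everolimus QD (3-8ng/mL) + prednisone QD for 6 months".

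In Appendix C2, the borderline, 1A and 1B-or-greater rows each tell staff to raise maintenance immunosuppression: "maximize MMF dosing, increase tacrolimus levels to upper limit of target range". Only the 1B-or-greater row adds a numerical floor: "tacrolimus levels must be ≥ 8 ng/mL at the time of last Thymoglobulin® dose". None of these rows mentions everolimus.

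Two other places bear on leaving the assigned regimen. Section 9 says: "The intervention will be withheld/discontinued for AE of grade 3 or higher or if requested by the study participant". It then adds pregnancy and graft loss, and does not name rejection. Section 7 says: "In case of subject withdrawal from study, the patient will return to standard of care medications". That sentence concerns withdrawal from the study, not rejection.

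**The concern.** Appendix C2 reads as an institutional protocol written for patients on tacrolimus and MMF. One of its later rows treats a move to an mTOR inhibitor as something still to be considered, while Arm 2 subjects already take one. Section 5.5 applies it unchanged to a trial arm built on a lower tacrolimus range and no MMF. Staff treating a 1B-or-greater rejection in Arm 2 must then depart either from the appendix or from the assigned regimen, and the protocol does not say which.

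Rejection of 1A or greater is a component of the secondary composite, and a difference in rejection rates is the first listed example of a reason to stop the study (Section 11.2). The conflict therefore falls on the arm and the event where consistent handling matters most.

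There is also a consequence for the primary comparison. Section 2.1 describes MMF as a twice-daily product. If MMF were added for an Arm 2 subject, that subject's Day 180 MMAS-8 score and adjunctive-drug medication possession ratio would no longer describe a purely once-daily regimen. With 20 subjects per arm, each such subject is 1/20 = 5% of the arm.

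**Working it through.** The plan gives no figure of its own on this point, so the check sets the texts side by side and then bounds how often the conflict could arise.

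**Text against text** (Section 4.1 against Appendix C2)

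| Instruction in Appendix C2 | Row | Arm 1: 5-12 ng/mL, with MMF | Arm 2: 2-5 ng/mL, no MMF |
|---|---|---|---|
| Tacrolimus to the upper limit of the range | 1A; 1B or greater | Can be met (12) | Can be met (5) |
| Tacrolimus at least 8 ng/mL | 1B or greater only | Can be met (5 < 8 < 12) | Cannot be met within the range (8 > 5) |
| Maximise MMF | 1A; 1B or greater | Applies | No MMF in the regimen |
| Everolimus | None | Not relevant | No instruction |
| Steroid, Thymoglobulin, blood counts, prophylaxis, adherence check, re-biopsy and clinic follow-up | As listed by row | Applies | Applies |

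Size of the tacrolimus gap in Arm 2: 8 - 5 = 3 ng/mL, and 8 / 5 = 1.6, so the floor is 60% above the top of the range. This concerns the 1B-or-greater row alone. In the 1A row only the MMF instruction fails to fit.

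**Does other text settle it?**
- Section 9 allows withholding or discontinuation for an adverse event of grade 3 or higher. It does not name rejection, assign it a grade, or refer to Appendix C2.
- Section 7 ties the return to standard of care to study withdrawal.
- Section 11.1 rules out deviations except to remove an immediate hazard, and does not rank the appendix against the arm definition.

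**How often it could arise in Arm 2** (expected number = rate x 20)
- Biopsy-proven acute rejection in the Envarsus table of Section 2.2, 1.2%: 0.012 x 20 = 0.24.
- Treated acute rejection in the everolimus table of Section 2.2, 16.2%: 0.162 x 20 = 3.24.
- Planning failure rate in Section 10.2, 20%: 0.20 x 20 = 4. This is an upper figure, because the composite also counts graft loss and death.

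The range is therefore about 0.2 to 4 subjects for any treated rejection. The two tables come from different regimens, and the everolimus trial ran 24 months against six here.

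The documents do not give the share of 1B or greater. Purely as an assumption, take a per-subject rate p from 1% to 10%. Then P(at least one of 20) = 1 - (1 - p)^20:
- p = 1%: 18%
- p = 2.5%: 40%
- p = 5%: 64%
- p = 10%: 88%

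**The case against.** Most of Appendix C2 is untouched. A reader might infer that the appendix as a whole cannot be followed in Arm 2. The documents do not support that: only the maintenance-immunosuppression line is affected, and the 8 ng/mL floor stands in one row.

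A reader might also count borderline rejection among the events that the protocol binds to the appendix. Section 5.4 starts acute rejection at 1A, so borderline cases fall outside the definition that Section 5.5 relies on, and outside the composite.

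It is tempting to say that following the appendix moves an Arm 2 subject to twice-daily MMF. The appendix says to maximise MMF. It does not say to start it in someone not taking it, or to stop everolimus. The effect on MMAS-8 is conditional on MMF being added.

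It could be argued that the appendix's target range means the standard-of-care range of 5-12 ng/mL, which would make its two tacrolimus instructions consistent with each other. The appendix does not define the term, and on that reading it would still contradict the Arm 2 range in Section 4.1.

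The grade 3 rule in Section 9 may offer an exit for severe cases, but nothing links it to rejection. Finally, Section 5.3 already requires doses of all immunosuppressants to be recorded, and Section 10.3 already includes all subjects under intention to treat, so neither is missing.

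These objections narrow the scope. None removes the contradiction for 1B or greater or the unmatched MMF instruction.

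**Conclusion.** The point holds in a limited form. For Banff 1B or greater, the tacrolimus floor in Appendix C2 lies 3 ng/mL above the top of the Arm 2 range and cannot be met on that regimen. For 1A and for 1B or greater, the MMF instruction has no counterpart in Arm 2. Both fit Arm 1, so the defect is confined to the experimental arm. No text says which instruction governs or how a resulting change is classified.

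The number of subjects affected is small and uncertain: about 0.2 to 4 of 20 in Arm 2 for any treated rejection, resting on rates borrowed from other regimens and follow-up periods, and fewer for the tacrolimus conflict. A reader might take 4 of 20 as the expected count. It is not: the 20% is a composite rate from a hypothetical 400-subject noninferiority calculation, and the Envarsus table in Section 2.2 points to a far lower number.

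The case for acting rests on a contradiction in a binding safety instruction that is cheap to remove, not on a large expected effect on the results.

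**What to change.** Reconcile Sections 4.1, 5.5 and 9 and Appendix C2 so that each arm has one non-contradictory instruction for maintenance immunosuppression during rejection. The investigators should decide its clinical content; no level, dose or drug is proposed here. In the same amendment, state whether a regimen change made because of rejection counts as intervention discontinuation under Section 9.

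Record the date of any such change alongside the doses already collected under Section 5.3, so that the Day 180 MMAS-8 and the possession ratio can be read against the regimen actually taken. No new rule on keeping subjects in the analysis is needed.

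Cost: a wording amendment and one CRF date field, with no extra visits or procedures.
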